14.16 Dispensing and Dosing of Blinded Study Drug

At Baseline (Day 1), eligible subjects will be dispensed bottles containing double-blind study medication supplies for 12 weeks (see [Section 12.3.2](#)). At Week 12, subjects will return all their bottles of study drug (see [Section 14.19](#)) and will be dispensed new supplies for an additional 12-week period.

Study drug will be taken as a single-day treatment repeated every 4 weeks (28 days [± 3]) for a total of 6 single-day treatments (Baseline [Day 1], Week 4, Week 8, Week 12, Week 16 and Week 20). The first dose of double-blind study drug will be administered at the study site (Baseline [Day 1]) and the remaining doses will be self-administered by the subjects at home, preferably with or immediately after a meal.

Whenever possible, on-site visits and phone contacts will be scheduled to occur on the date of dosing to facilitate reminding subjects to take their study drug dose. It is recommended that each subject identifies and keeps their optimal routine to facilitate compliance (for example, administering the study drug after breakfast and after dinner on dosing days). An electronic dosing reminder system (e.g. text message) may be implemented for consenting subjects to facilitate study drug dosing compliance. Details of study treatment groups and dietary requirements for treatment administration are provided in [Section 12.1.2](#) and [Section 12.2](#), respectively.

14.17 Assessment of Quality of Life

QOL will be assessed at Day -14, Baseline (Day 1), Week 12, Week 24 (TOC) and Week 36 (EOFU). Quality-of-life tools will include the Euro Quol 5 Dimensions (EQ-5D), Short Form Health Survey (SF-36) and Female Sexual Distress-Revised Scale (FSDS).

14.18 Assessment of Potential Recurrence and Use of Rescue Antifungal Medication

The occurrence of a recurrence is the key efficacy parameter in this study. Randomized subjects will be assessed for potential recurrence at all visits during the Prevention of Recurrence Phase following Day 1 (Baseline) (i.e., from Day 2 through Week 36 [EOFU]), including phone

contacts, scheduled visits and unscheduled visits, as well as in between visits. If during a phone contact or at any other time there is suspicion of a potential recurrence (any kind of recurrence, i.e., Mycologically Proven, Presumed or Suspected), subjects will be instructed to visit the study center for a proper evaluation of their recurrence before initiating any VVC treatment.

14.18.1 Categories of Recurrences

In this study, Recurrences of VVC will be broken into three categories:

- **Mycologically Proven Recurrence:** An episode of VVC with a total composite score ≥ 3 on the VSS Scale and a culture positive for *Candida* spp. that required antifungal treatment.
- **Presumed Recurrence:** An episode of VVC with a total composite score ≥ 3 on the VSS Scale that required antifungal treatment and for which there is a positive KOH microscopy but no positive fungal culture.
- **Suspected Recurrence:** An episode of VVC that required treatment with an antifungal agent (including self-administration with over-the-counter antifungals) regardless of VSS composite score but for which there is no mycological evidence of disease, such as a positive KOH microscopy or fungal culture.

14.18.2 Procedures for Potential Recurrences

Potential recurrences will be assessed based on clinical and mycological outcomes and need for other antifungal treatment. If a subject has symptoms suggestive of *Candida* infection (itching, burning, irritation) that in the opinion of the investigator may require antifungal therapy, the following procedures must be completed:

- Rate and document symptoms in the eCRF ([Section 14.9](#)),
- Perform vaginal examination to rate signs and document in the eCRF ([Section 14.8](#)),
- Measure vaginal pH at the site and document results in the eCRF ([Section 14.7](#)),
- Collect vaginal sample for KOH testing and investigation of potential bacterial vaginosis and *Trichomonas vaginalis* infection at the site or by the local laboratory ([Section 14.7](#)),
- Collect vaginal samples for fungal culture by the central laboratory ([Section 14.7](#)), and
- Document any additional antifungal treatment used by the subjects ([Section 14.21](#)).

All of the procedures above should be completed prior to administration of rescue antifungal medication. **Subjects participating in the study should be strongly discouraged from self-administering any treatment for a potential recurrence.** Ideally, if the severity of the symptoms allows based on the investigator's judgment, the initiation of antifungal therapy should be delayed until results from the vaginal culture are available to confirm that the episode is due to *Candida* spp. and not to other cause of vaginitis.

The following steps should be followed for potential recurrences:

- If the vaginal culture results are positive for yeast and the subject remains symptomatic (VSS score ≥ 3), rescue antifungal therapy should be offered and the episode should be listed as a Mycologically Proven Recurrence. Rescue antifungal therapy should be documented in the eCRF.
- If the vaginal culture results are negative for yeast, other causes of vaginitis (e.g. bacterial vaginitis or trichomoniasis) should be further investigated and rescue antifungal therapy may not be indicated. Subjects with a diagnosis of vaginitis caused by pathogens other than yeast (e.g. bacterial vaginitis or trichomoniasis) may receive treatment for these conditions as indicated and the vaginitis episode should be listed as AE.
- If the vaginal culture results are negative for yeast but the patient was given rescue antifungal therapy based on KOH results and symptoms (VSS score ≥ 3), the episode should be listed as a Presumed Recurrence. The rescue antifungal therapy administered should be documented in the eCRF.
- Empiric administration of rescue antifungal therapy prior to collecting and documenting evidence that the vaginal symptoms are caused by *Candida* spp. infection is strongly discouraged. Subjects who receive empiric rescue antifungal therapy for a potential recurrence of VVC prior to documenting the *Candida* spp. infection should still have their vaginal evaluation including KOH and culture collected as soon as possible. These episodes should be listed as Suspected Recurrences.
- If subjects experience a relapse of the VVC symptoms, they should be strongly discouraged from self-administering any treatment for VVC and instructed to visit the study site for evaluation of the episode and prescription of rescue therapy, if needed.
- In the event that the subject self-administers, or another physician prescribes therapy for a recurrent episode of VVC, the subject should still be seen at the study site as soon as possible for an unscheduled visit, which should include collection of a vaginal swab for culture.

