If during a phone contact or at any other time there is suspicion of a potential recurrence (any kind of recurrence, i.e., Mycologically Proven, Presumed or Suspected), subjects will be strongly discouraged from self-administering any treatment and will be instructed to visit the study center immediately for collection of vulvovaginal samples before initiating any VVC treatment. Procedures for collecting and processing local samples, as well as for shipping central laboratory vulvovaginal samples, will be described in the laboratory manual.

14.8 Vulvovaginal Examination and Rating of Signs by the Investigator Using the VSS Scale

The investigator (or qualified designee) will perform vulvovaginal examinations to rate the subject's signs of infection at Screening, Baseline (Day 1), Week 12 and Week 24 (TOC). The signs of infection will also be rated at Week 4, Week 8 and Week 36 (EOFU) if symptoms are present and any time there is suspicion of a potential recurrence. A vulvovaginal examination should be scheduled immediately if there is suspicion of a potential recurrence based on a phone contact discussion or at any other time (see [Section 14.18](#)). The investigator should ensure that subjects rate their symptoms of infection at the site every time that the investigator performs a vulvovaginal examination for the rating of signs.

Investigators will assess the signs of infection using the VSS Scale provided in [Section 21.0](#) [[Appendix B](#)]), a standardized, predefined scale where each sign of the vagina and/or vulva will be given a numerical rating based on severity, as follows:

- Edema: absent = 0; mild = 1; moderate = 2; severe = 3
- Erythema: absent = 0; mild = 1; moderate = 2; severe = 3
- Excoriation or fissures: absent = 0; mild = 1; moderate = 2; severe = 3

Other findings will be recorded using the most relevant medical term in the abbreviated physical examination page of the eCRF.

If a subject is actively menstruating at the time of an on-site study visit that requires a vulvovaginal exam, the visit should be rescheduled as soon as the subject's period ends but in no case more than 7 days after the initially scheduled visit.

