14.9 Rating of Vulvovaginal Symptoms by the Subject Using the VSS Scale

Subjects will be asked to rate their vulvovaginal symptoms at Screening, from Day -14 through Day -1 of the Acute Phase, and then from Day 1 (Baseline) through Week 36 (EOFU) of the Prevention of Recurrence Phase. Subjects will also assess their symptoms at unscheduled visits, if applicable.

Subjects will rate their symptoms of infection using the VSS Scale (see [Appendix B](#)), where each vulvovaginal symptom will be given a numerical rating based on severity, as follows:

- Itching: absent = 0; mild = 1; moderate = 2; severe = 3
- Burning: absent = 0; mild = 1; moderate = 2; severe = 3
- Irritation: absent = 0; mild = 1; moderate = 2; severe = 3

From Baseline (Day 1) through the Week 36 (EOFU) visit, subjects will rate their symptoms and record their scores on the VSS Scale included in their subject diaries. Symptoms of infection will be rated on a weekly basis and at the time of each scheduled or unscheduled visit to the site.

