14.18.3 Rescue Antifungal Therapy

Subjects will be offered one dose of fluconazole 150 mg as rescue therapy. Other antifungal rescue therapy may be administered, per investigator's discretion, based on the *Candida* species reported from the culture results. All antifungal therapy administered during the study should be documented in the EDC, with the reason for use clearly indicated (i.e., Mycologically Proven Recurrence, Presumed Recurrence or Suspected Recurrence).

If a subject experiences one or more recurrences during the Study Treatment Period (i.e., a Mycologically Proven Recurrence, a Presumed Recurrence or a Suspected Recurrence), she will continue her scheduled study drug administration and will complete all scheduled visits until reaching EOFU.

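### Protocol 14.18.2 lists empirically rescued episodes as Suspected whatever their KOH and culture show, against 14.18.1 and SAP 8.1, and the SAP does not state the source of the category or which VSS counts after rescue

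*Protocol*

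**What the plan says.** Protocol 14.18.1 sorts recurrences by data. Proven needs a VSS of at least 3, a positive culture and a need for antifungal treatment. Presumed needs the same score and need for treatment, with a positive KOH but no positive culture. Suspected is a treated episode "for which there is no mycological evidence of disease, such as a positive KOH microscopy or fungal culture". None of the three depends on whether rescue came before or after the tests.

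Protocol 14.18.2 asks for the work-up first: "All of the procedures above should be completed prior to administration of rescue antifungal medication". It strongly discourages empiric rescue. If empiric rescue is given anyway, subjects "should still have their vaginal evaluation including KOH and culture collected as soon as possible", and the next sentence reads: "These episodes should be listed as Suspected Recurrences". That sentence sets no condition on the results.

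Protocol 14.18.3 has the site record each antifungal use with one of the three categories as its reason.

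SAP 8.1 repeats the 14.18.1 definitions and adds one rule: a treated episode with a VSS below 3 is Suspected whatever the mycology. That rule is not in Protocol 14.18.1 and is not among the changes listed in SAP 11.

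**The concern.** An empirically rescued episode with a VSS of 3 or more and a positive KOH or culture has one category under 14.18.2 and another under 14.18.1 and SAP 8.1. Sites following 14.18.2 will enter Suspected. SAP 8.1 does not say that a category derived from the data replaces that entry.

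Derivation leaves a second gap. If rescue came before any complete examination, the only composite VSS for the episode is one taken after treatment, and the SAP does not say whether it counts.

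Four analyses depend on the category: the key secondary endpoint (no Mycologically Proven Recurrence up to Week 24), the Proven-or-Presumed endpoints, time to first Proven recurrence, and the table of failures by recurrence category. For each of them, a choice that changes the counts is left open.

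**Working it through.** **Step 1. The rules side by side, for an empirically rescued episode.**

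| Findings | Protocol 14.18.1 | SAP 8.1 | Protocol 14.18.2 |
|---|---|---|---|
| VSS ≥ 3, culture positive | Proven | Proven | Suspected |
| VSS ≥ 3, KOH positive, no positive culture | Presumed | Presumed | Suspected |
| VSS ≥ 3, no positive test | Suspected | Suspected | Suspected |
| VSS < 3, positive KOH or culture | no category fits | Suspected | Suspected |
| VSS < 3, no positive test | Suspected | Suspected | Suspected |

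The conflict lies in the first two rows. The fourth row shows why the unlisted VSS < 3 rule belongs in the protocol definitions or in SAP 11.

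Self-treated and externally prescribed episodes have their own step in 14.18.2, which sets no category, so the label conflict does not reach them. The VSS gap in Step 2 can.

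**Step 2. Which VSS is available.** The composite needs signs and symptoms. Signs come only from an examination (Protocol 14.8: "Investigators will assess the signs of infection using the VSS Scale"). The diary holds symptoms alone (Protocol 14.9: "Symptoms of infection will be rated on a weekly basis and at the time of each scheduled or unscheduled visit to the site"). SAP 8.2.4 does not calculate the score if an item is missing, except for symptom-free subjects with no suspected recurrence at Weeks 4, 8 and 36. So rescue before any complete examination leaves only a post-rescue composite. If that is below 3, SAP 8.1 makes the episode Suspected even with a positive culture. The worst-value rule in SAP 8.2.4 works within a visit and does not mention rescue. The rescue rule in SAP 4.4.2 covers quality of life only.

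**Step 3. The plan's own figure.** Protocol 18.1 and SAP 4.1 state 90% power with about 240 subjects, 65% v 43%, by Fisher's exact test. Exact enumeration at 120 per arm, two-sided 5%, gives 90.9%, so the figure reproduces. All three categories are failures, so the 22-point primary difference does not move. The planned failure rates are 1 − 0.65 = 35% and 1 − 0.43 = 57%.

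**Step 4. Illustration for the key secondary endpoint.** The documents give neither the Proven share of failures nor the empiric-rescue share. Both are assumed.

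- Proven proportion in an arm = q × F × (1 − s), where F is 0.35 or 0.57, q is the assumed Proven share of failures (the same in both arms, no imputed failures), and s is the share of those subjects relabelled Suspected.
- Difference = placebo Proven minus ibrexafungerp Proven.
- Relative risk (RR) of no Proven recurrence = (1 − ibrexafungerp Proven) / (1 − placebo Proven). SAP 8.1.1 presents the relative risk.

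At q = 80% with no relabelling, 0.8 × 35% = 28.0% and 0.8 × 57% = 45.6%. The difference is 17.6 points and RR = 0.720 / 0.544 = 1.32. With 20% relabelled in both arms, the proportions are 22.4% and 36.48%. The difference is 14.1 points and RR = 0.776 / 0.6352 = 1.22.

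| Relabelled (ibrexafungerp, placebo) | q = 80%: points, RR | q = 60%: points, RR |
|---|---|---|
| 0%, 0% | 17.6, 1.32 | 13.2, 1.20 |
| 10%, 10% | 15.8, 1.27 | 11.9, 1.17 |
| 20%, 20% | 14.1, 1.22 | 10.6, 1.15 |
| 0%, 20% | 8.5, 1.13 | 6.4, 1.09 |
| 20%, 0% | 23.2, 1.43 | 17.4, 1.26 |

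At q = 80%, relabelling 20% means 0.2 × 0.28 × 120 ≈ 7 subjects on ibrexafungerp and 0.2 × 0.456 × 120 ≈ 11 on placebo.

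**Step 5. Direction under unequal relabelling.** The difference grows when s(ibrexafungerp) × 35 > s(placebo) × 57, a share ratio above 57/35 = 1.63. RR grows when the ratio exceeds [0.57 / (1 − 0.57q)] / [0.35 / (1 − 0.35q)]:

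- q = 80%: (0.456 / 0.544) / (0.28 / 0.72) = 2.16
- q = 60%: (0.342 / 0.658) / (0.21 / 0.79) = 1.96

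No power is quoted, because the documents state no power target for this endpoint.

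**The case against.** The best defence is that SAP 8.1 already defines the categories by VSS, KOH, culture and treatment, and that no passage says the analysis uses the site-entered reason. On that view only a clarification is missing. This largely stands for the SAP: derivation is the natural reading. It does not remove the contradiction in the protocol, and it leaves the VSS gap open.

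The practice is also discouraged and sampling is required before rescue, so the episodes may be few. That stands. However, the phrase about rescue before the infection is documented can also cover rescue given after sampling but before the central culture result. 14.18.2 asks sites to wait for that result only ideally, if severity allows. Such episodes have a pre-rescue composite, so the VSS gap is confined to rescue before any complete examination.

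The illustration uses assumed shares and ignores the failure imputation of SAP 4.4.1. The one-arm rows have no stated mechanism in a double-blind trial and serve only as bounds.

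Two stronger readings are tempting and not supported:

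- A reader might infer that the first listing step of 14.18.2, where "the episode should be listed as a Mycologically Proven Recurrence", is contradicted as well. That step has a positive culture, persisting symptoms and rescue then being offered, so it presupposes that rescue has not been given. General step and exception is the natural reading. The conflict is with 14.18.1 and SAP 8.1.
- A reader might take 1.63 as the tipping point for bias on any scale. It holds for the difference only. At q = 80% with 18% v 10% relabelled (ratio 1.8), the difference rises from 17.6 to 18.1 points while RR falls from 1.32 to 1.31.

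**Conclusion.** The concern holds for the category-based endpoints. Protocol 14.18.2 gives a category that 14.18.1 and SAP 8.1 contradict for empirically rescued episodes with a VSS of 3 or more and positive mycology. The SAP settles neither the source of the category nor the VSS to use when none precedes rescue.

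The size is unknown and may be small. On the assumptions shown, equal relabelling of 20% costs 3.5 points at 80% Proven (17.6 to 14.1) and 2.6 points at 60% (13.2 to 10.6; RR 1.20 to 1.15). Unequal relabelling could bias the result either way. It favours ibrexafungerp only above a share ratio of 1.63 on the difference scale, or about 2.16 (80% Proven) or 1.96 (60% Proven) on the relative-risk scale.

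A reader might infer that the primary result or the sample size is in doubt, or that the analysis will use the site label. The documents support neither. This should be settled before unblinding, but it does not threaten the main conclusion of the trial.

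**What to change.** 1. Reconcile the listing sentence in Protocol 14.18.2 with 14.18.1, so that these episodes are classified from the VSS, KOH and culture obtained. Add the VSS < 3 rule to 14.18.1 and the other copies of the definition (synopsis, 7.2.3, 10.1.1.3.3, 18.6.1), or list it in SAP 11.
2. In SAP 8.1, before unblinding, state that the analysis category is derived from the recorded VSS, KOH, culture and antifungal data, not from the site-entered reason for use. State which composite VSS counts, for example the last complete score of the episode before rescue or, failing that, the first after it, flagged as post-rescue. State how same-day scores and episodes with no complete score are handled.
3. Optionally, add a sensitivity analysis of the key secondary endpoint that counts these episodes as Suspected, if the data allow them to be identified. The documents name the reason for use (14.18.3) and start and stop dates (14.21), but not who gave the rescue or its order within a day.

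Items 1 and 2 cost a few sentences in the protocol or site instructions and in the SAP. Item 3 costs one table, and possibly data that the documents do not say are collected. One limit remains: samples taken after rescue may miss yeast, so some true recurrences could stay Suspected under either rule. The change concerns classification only; no treatment rule is altered.

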14.18.3 Rescue Antifungal Therapy

Subjects will be offered one dose of fluconazole 150 mg as rescue therapy. Other antifungal rescue therapy may be administered, per investigator's discretion, based on the *Candida* species reported from the culture results. All antifungal therapy administered during the study should be documented in the EDC, with the reason for use clearly indicated (i.e., Mycologically Proven Recurrence, Presumed Recurrence or Suspected Recurrence).

If a subject experiences one or more recurrences during the Study Treatment Period (i.e., a Mycologically Proven Recurrence, a Presumed Recurrence or a Suspected Recurrence), she will continue her scheduled study drug administration and will complete all scheduled visits until reaching EOFU.

